5.6.3.2. Logistic model

The following pregnancy outcomes will be analysed using logistic regression model:

- Stillbirth
- Live birth
- Full term delivery
- Pre-term delivery
- Post-term delivery
- Small for gestational age at birth
- Large for gestational age at birth
- Baby’s death during the first 12 weeks of life
- Birth defect

Logistic regression models will be computed using the SAS LOGISTIC procedure. The models will included the pregnancy outcome as a binary dependent variable, the exposure status as a binary independent variable and the age at first day of gestation as a continuous covariate. The OR and its 95% Wald CI will be derived. Other covariates will not be included in the model.

In case of less than 10 cases of a specific outcome, the logistic regression analysis will not be carried out on this outcome.

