5.5.2. Demographic and baseline characteristics

Demographic and baseline characteristics of all included subjects (age at first day of gestation, age at vaccination, marital status, smoking, alcohol consumption, region (GP practice)) will be summarized per cohort and overall, using descriptive statistics.

Frequency tables will be generated for categorical variables.

Mean, standard error, median and range, will be provided for continuous variables.

Medical condition during pregnancy (diabetes, high blood pressure) will be summarized in a frequency table.

Availability of data in CPRD **GOLD** will be summarized by descriptive statistics: proportion of Baby and Mother links.

Proportion of subjects with first day of LMP before, during and after H1N1 pandemic in the UK (June 1st 2009 to February 28th 2010 according to Pebody [Pebody, 2010]).

The two cohorts will be compared for their demographic and baseline characteristics using Fisher's exact test or Student t-test.

(Amended 14 March 2013)

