5.5.3.2. Other endpoints

All other endpoints are binary variables: stillbirths, live births, full term delivery, pre-term and post-term delivery, small for gestational age, large for gestational age, birth defects and baby's death.

The proportion of each outcome will be computed for the exposed and non-exposed cohorts as the number of cases divided by the total number of subjects with known pregnancy outcome. An exact 95% CI will be computed.

The exposed and non-exposed cohorts will be compared using logistic regression with the pregnancy outcome as the dependent variable, a dichotomous exposure as the independent variable and the age at first day of gestation as a covariate. The odds ratio (OR) and its 95% CI will be derived.

Baby characteristics will be summarized per cohort using descriptive statistics: n of non-missing observations, mean, standard deviation, minimum and maximum for continuous variables (birth weight and length) and frequency table (n, %) for categorical variables (sex, Apgar score at 1 and 5 min).

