5.6. Statistical calculations

All the statistical calculations will be done in SAS 9.2 or higher.

All the statistical tests will be two-sided at alpha level of 0.05.

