5.6.2. Descriptive statistics

Age at first day of gestation will be summarized by descriptive statistics per cohort (exposed and non-exposed) and overall: n of subjects, mean, standard deviation (SD), median, minimum and maximum and compared between the two cohorts using a student t-test.

Smoking status (smoker vs. non-smoker), alcohol consumption (Yes/No) will be summarized in frequency tables (n, %) per cohort and overall. The two cohorts will be compared using a Fisher's exact test.

Diabetes and high blood pressure will be summarized in frequency tables (n, %) per cohort and overall. The two cohorts will be compared using a Fisher's exact test.

First day of LMP occurring during the H1N1 pandemic (01JUN2009 to 28FEB2010) will be summarized in frequency tables (n, %) per cohort and overall. The two cohorts will be compared using a Fisher's exact test.

Exposure to other vaccines will also be summarized in frequency tables per cohort and period (within 3 months before first day of gestation and during the 1st trimester of gestation).

Number of subjects exposed to contra-indicated drugs during the 1st trimester of gestation will be tabulated per cohort and overall.

All the pregnancy outcomes (see section 5.2.4.2) and birth defects (see section 5.2.4.3) will be summarized by descriptive statistics per cohort. The statistics will be computed:

- Number of cases
- Proportion computed as the number of cases divided by the total number of pregnancies

All the cases of pregnancy outcome including outcomes with apparent birth defects and baby's deaths will be listed with data about exposure status, age at first day of gestation, gestational age at the event date, smoking status, alcohol consumption, diabetes, high blood pressure, exposure to other vaccines, to contra-indicated drugs and H1N1 pandemic.

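### Below 10 cases the only planned between-cohort comparison of stillbirth, baby's death or birth defect is dropped, and no substitute is named

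*Combined protocol and SAP*

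**What the plan says.** Section 5.5.3.2 covers every endpoint other than spontaneous abortion: "The exposed and non-exposed cohorts will be compared using logistic regression with the pregnancy outcome as the dependent variable". Age at first day of gestation is the covariate, and no minimum number of cases is stated. The same section gives each cohort's proportion, over women with known pregnancy outcome, an interval: "An exact 95% CI will be computed".

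Section 5.6.3.2 lists nine outcomes for this model, among them stillbirth, baby's death within 12 weeks and birth defect. On estimation it says "The OR and its 95% Wald CI will be derived", and on adjustment beyond age "Other covariates will not be included in the model". It closes with the cancellation rule: "In case of less than 10 cases of a specific outcome, the logistic regression analysis will not be carried out on this outcome". It does not say whether the 10 cases are counted over both cohorts or within one, or separately for each risk window.

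Section 5.6.2 adds counts, proportions and a listing of every case with its exposure status. The exact between-cohort test in the plan is for baseline variables: "The two cohorts will be compared for their demographic and baseline characteristics using Fisher" (the sentence goes on to name the exact test and the t-test). Nothing equivalent is named for a sparse outcome.

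**The concern.** Assessing the other pregnancy outcomes is a secondary objective for both risk windows (section 2.2), in a study designated a Targeted Safety Study and a PASS (section 3). The outcomes most likely to fall under the rule are the rarest, and these include the gravest. Under the text as it stands, a cohort imbalance in smoking gets a test, while an imbalance in stillbirth or infant death may get neither an estimate nor a test.

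Fewer than 10 cases do not make a comparison impossible. They make a large-sample model unreliable, which is a reason to change method. Any comparison added after the counts are known would be a post hoc choice, to be described and justified as a deviation under section 5.7.

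Sections 5.5.3.2 and 5.6.3.2 also disagree on whether the comparison is always made.

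**Working it through.** **Inputs.** Section 3.2 (feasibility): 243 exposed (-30 to +45 days), 379 exposed (-30 to +90 days), 667 non-exposed. Totals: 243 + 667 = 910 and 379 + 667 = 1046. The threshold of 10 and the Wald interval come from section 5.6.3.2. The plan gives no rate for stillbirth, baby's death or birth defect, so the rates below are assumptions. The count is taken over both cohorts, which is also an assumption.

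**The plan's own figures.** The only power figures (98% and 99%, section 5.4) concern spontaneous abortion. They reproduce as 0.978 and 0.993 with Freedman's log-rank formula for unequal groups, 20% dropout, and 2.0 read as a risk ratio. There is no figure to reproduce for the logistic endpoints.

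**Step 1: how often the rule applies.** P(fewer than 10 cases) = sum over k = 0 to 9 of C(N,k) r^k (1-r)^(N-k).

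| Assumed rate r | N = 910 | N = 1046 | N = 546 (60% of 910) |
|---|---|---|---|
| 0.5% | 0.98 | 0.96 | 0.999 |
| 1% | 0.57 | 0.40 | 0.95 |
| 1.5% | 0.13 | 0.05 | 0.69 |
| 2% | 0.01 | 0.003 | 0.35 |

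Ten expected cases need r = 10/910 = 1.10% or 10/1046 = 0.96%. The last column assumes that only 60% of women contribute. It matters because section 3.2 says the feasibility counts do not apply all eligibility criteria, section 5.5.3.2 restricts to known outcomes, and baby's death can occur only after live birth.

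**Step 2: what would go uncompared.** Exact conditional analysis of the 2x2 table:

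| Exposed v non-exposed cases | Denominators | OR | Exact 95% CI | Fisher p |
|---|---|---|---|---|
| 6 v 3 | 243:667 | 5.6 | 1.18 to 34.8 | 0.014 |
| 5 v 4 | 243:667 | 3.5 | 0.74 to 17.7 | 0.062 |
| 4 v 5 | 243:667 | 2.2 | 0.44 to 10.4 | 0.26 |
| 6 v 3 | 379:667 | 3.6 | 0.75 to 22.1 | 0.079 |

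For the first row, the sample OR is (6 x 664)/(3 x 237) = 5.6. In that row the planned output would be 6/243 = 2.5% (0.9% to 5.3%) against 3/667 = 0.4% (0.1% to 1.3%). These intervals overlap although the exact OR interval excludes 1.

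**Step 3: chance of losing a significant comparison.** With an assumed 0.5% rate in the non-exposed and all women contributing:

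| Denominators | True OR | P(fewer than 10 cases) | P(fewer than 10 cases and Fisher p <= 0.05) |
|---|---|---|---|
| 243:667 | 3 | 0.84 | 0.22 |
| 243:667 | 5 | 0.55 | 0.30 |
| 379:667 | 3 | 0.59 | 0.15 |
| 379:667 | 5 | 0.19 | 0.10 |

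**Step 4: the Wald interval at 10 or more cases.** With 10 to 20 cases, true OR 1 to 3 and cases in both cohorts, exact enumeration gives coverage of 0.94 to 0.98. Simulation of the age-adjusted model at 243:667 gives 0.97 (OR 1) and 0.96 (OR 3). Failure needs all cases in one cohort. With 10 cases and no effect, P(none exposed) = (667/910)^10 = 0.045, or (667/1046)^10 = 0.011; P(all exposed) is negligible. The exact interval remains usable there: for 0 v 10 its upper limit is 1.22 (243:667) or 0.78 (379:667). Borderline conclusions can differ: 6 v 4 at 243:667 gives Wald 1.17 to 15.0 and exact 0.98 to 20.4.

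**The case against.** Descriptive reporting of very sparse secondary outcomes is a recognised choice. The objective is worded as assessing risk, and the formal hypotheses in section 5.3 concern spontaneous abortion only. The exact per-cohort intervals and the full listing by exposure survive the rule, so a 6 v 3 split would be visible to any reader. Less extreme splits, and the same split in the wider window, would not be significant. An exact OR would also lose the adjustment for age, the only covariate planned for these endpoints, when section 3.2 expects the cohorts to differ by about one year.

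Most of this stands. It limits the consequence and the severity, and the loss of age adjustment must be stated as a cost. It does not fill the gap: separate intervals are not a comparison and can mislead by overlapping, and section 5.5.3.2 does promise a comparison.

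A reader might go further and infer that the Wald intervals make the comparison invalid even at 10 or more cases, or that every outcome should move to penalised likelihood. Step 4 does not support the first: coverage is close to or above nominal, and the failure is confined to all cases falling in one cohort. The second would be preference. Nothing here shows a problem for more common outcomes on the same list.

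**Conclusion.** The point holds in a limited form. Section 5.6.3.2 withdraws the between-cohort comparison below 10 cases without a substitute, contradicts the unconditional statement in section 5.5.3.2, and leaves the case count undefined. For an outcome near 0.5% the comparison is almost certain to be dropped (0.98 and 0.96 for the two windows). Near 1% it is roughly even (0.57 and 0.40), and at 2% it is unlikely (0.01 and 0.003) unless far fewer women contribute.

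These figures rest on assumed rates, on unreduced feasibility denominators and on counting cases over both cohorts. Smaller denominators or a per-cohort count would make cancellation more frequent.

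It would be too strong to say that a safety signal would be concealed, since proportions, exact intervals and listings remain. What is missing is a pre-specified estimate of the difference with its uncertainty. This is worth correcting because it is cheap. It concerns secondary endpoints and leaves the primary Cox analysis untouched.

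**What to change.** In section 5.6.3.2, replace the cancellation rule with the following:

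- When an outcome has fewer than 10 cases over the two compared cohorts in the given risk window, or when all its cases fall in one cohort, report the exact conditional OR with exact 95% CI, labelled as unadjusted for age. An age-adjusted Firth OR with profile-likelihood CI may be added as support.
- Otherwise keep the planned age-adjusted logistic model with Wald CI.

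Amend section 5.5.3.2 to refer to this rule, so that the two sections agree. Keep the per-cohort exact intervals and the case listings.

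The cost is the EXACT statement (and, if wanted, the FIRTH option) in the SAS LOGISTIC procedure already planned, plus one table row per affected outcome. The downsides are wide intervals for the rarest outcomes and no age adjustment in the exact estimate.

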5.7. Conduct of analyses

Any deviation(s) or change(s) from the original statistical plan outlined in this protocol will be described and justified in the final study report.

5.7.1. Sequence of analyses

All the analyses will be done on the final database.

5.7.2. Statistical considerations for interim analyses

There is no interim analysis.

5.8. Changes from planned analyses

Not applicable.

6. SERIOUS ADVERSE EVENTS

This study intends to collect data only on pregnancies and their outcomes. Where required, the results of this study will be communicated to regulators when the final study report becomes available.

7. CONDUCT OF THE STUDY

7.1. Regulatory and ethical considerations, including the informed consent process

The study will be conducted in accordance with all applicable regulatory requirements.

The study will be conducted in accordance with the Guidelines for Good Pharmacoepidemiology Practices (GPP) [ISPE, 2007] all applicable subject privacy requirements and the guiding principles of the Declaration of Helsinki.

Conduct of the study includes, but is not limited to, the following: CPRD *GOLD*'s Independent Scientific Advisory Committee (ISAC) review and favourable opinion/approval of study protocol and any subsequent amendments. Of note, ISAC has approved the study design on 18 January, 2012 (see Appendix C).

No patient informed consent will be obtained. The patient information in the CPRD *GOLD* database is fully coded and GSK Biologicals personnel will not be able to make a link between the data and specific individuals.

The CPRD *GOLD* has an ethical approval from a Multi-centre Research Ethics Committee (MREC) for purely observational research (i.e. studies that do not include patient involvement, [CPRD *GOLD*, 2012]).

(Amended 14 March 2013)

7.2. Data privacy

The CPRD *GOLD* database is a fully coded, MHRA-approved database with an international reputation in the field of drug safety signal evaluation [Williams, 2012].

GSK has a licence to use this database from CPRD *GOLD*, in order to perform analyses. GSK has access to an online extract from CPRD *GOLD* which is continuously updated. Data will be not identifiable by GSK as the key-codes are maintained by CPRD *GOLD* and are not available online and are never shared with external parties. When GSK requests medical chart review to CPRD *GOLD*, CPRD *GOLD* has internal processes to secure the maintenance of confidentiality concerning subject identifiers. Identifiers will never be transferred to GSK.

(Amended 14 March 2013)

7.3. Biological Sample handling and analysis

No samples will be collected in this study.

7.4. Remote Data Entry instructions

Remote Data Entry (RDE), using a validated computer application developed by GSK (En@ble), will be used by the GSK identified reviewer to enter the information obtained from the free text review and final case ascertainment classification.

In all cases, subject initials will not be collected nor transmitted to GSK. Subject data necessary for analysis and reporting will be entered/transmitted into a validated database or data system. Clinical data management will be performed in accordance with applicable GSK standards and data cleaning procedures.

No monitoring will be done. The GSK identified reviewer remains accountable for the data entry.

8. ADMINISTRATIVE MATTERS

To comply with GPP or other applicable guidelines administrative obligations relating to data collection, archiving data, audits, confidentiality and publications must be fulfilled.

8.1. Audits

To ensure compliance with GPP or other applicable guidelines and all applicable regulatory requirements, GSK may conduct a quality assurance audit. Regulatory agencies may also conduct a regulatory inspection of this study. Such audits/inspections can occur at any time during or after completion of the study. If an audit or inspection occurs, the database owner agrees to allow the auditor/inspector direct access to all relevant documents and to allocate his/her time and the time of his/her staff to the auditor/inspector to discuss findings and any relevant issues.

8.2. Posting of information on public registers

Study information from this protocol will be posted on public registers (e.g. GSK Clinical Study Register, clinicaltrials.gov) before the start of analysis as applicable.

8.3. Ownership and publication

8.3.1. Ownership

The source data are the property of the UK Secretary of State. GSK has received the authorisation to use this data for study purposes. All information provided by GSK and data generated as a result of the analysis are property of GSK.

8.3.2. Posting to the clinical trials registers and publication

The results summary will be posted to the GSK Clinical Study Register and other public registers as applicable, in accordance with regulatory and policy mandated timelines. In addition, a manuscript will be submitted to a peer reviewed journal for publication within the policy defined timelines. The manuscript will be co-authored by the CPRD **GOLD** Research Group and coordinated by GSK. When manuscript publication in a peer-reviewed journal is not feasible, further study information will be posted to the GSK Clinical Study Register (e.g. write-up).

(Amended 14 March 2013)

10. APPENDICES

Appendix A Algorithms and medical codes for data extraction

Appendix B Templates of tables and figures

Appendix C Feedback from ISAC

Appendix D Amendments and administrative changes to the protocol

GlaxoSmithKline Biologicals
 
Clinical Research & Development
 
Protocol Amendment 1
	
eTrack study number and Abbreviated Title	114101 (EPI-HPV-018 VS UK DB)
Amendment number:	Amendment 1
Amendment date:	14 March 2013
Co-ordinating author:	Co-ordinating authors' names retracted to protect Subject Privacy

Rationale/background for changes: This protocol has been amended for the following reasons:
 
 • In section 5.2.4.2. Pregnancy outcomes and section 5.2.6. Final case ascertainment step, review of pregnancy outcomes by the GSK safety physician and by experts has been updated. • In section 5.2.5.1. First day of LMP, the length of pregnancy has been modified to fit the United Kingdom (UK) definition (280 days) and not the French definition (283 days). • Clinical Practice Research Datalink (CPRD) has been replaced by Clinical Practice Research Datalink General Practitioner OnLine Database (CPRD GOLD). • Section 1.2. Rationale for the study has been updated with recent published data about Cervarix uptake in the United States (US) and about Cervarix safety in the UK. • In section 3. Study design, the number of subjects in the exposed cohort in the epoch table has been corrected. • Section 3.1. HPV vaccine coverage and pregnancy rate in the UK teenagers has been updated with recent published data about HPV vaccine coverage in the UK. • In section 5.6.3.1. Cox proportional hazards model, enrolment from CPRD has been replaced by de-enrolment from CPRD GOLD. • Contributing authors have been updated. 
Other changes were made for simplification, clarification or consistency.
	

Amended text has been included in *bold italics* in the following sections:

Cervarix has been written in italics throughout the synopsis.

Clinical Practice Research Datalink has been replaced by Clinical Practice Research Datalink General Practitioner OnLine Database throughout the document.

CPRD has been replaced by CPRD GOLD throughout the document, including Appendices A and B.

- **Other contributing authors (GSK Biologicals)**

Contributing authors' names retracted to protect Subject Privacy

- **List of abbreviations**

GP: General Practitioner

ISAC: Independent Scientific Advisory Committee ~~from CPRD~~ (*for Medicines and Healthcare products Regulatory Agency database research*)

- **Glossary of terms**

Independent Scientific Advisory Committee (ISAC): ~~CPRD's~~ Independent Scientific Advisory Committee *for Medicines and Healthcare products Regulatory Agency database research*.

- **Section 1.2. Rationale for the study**

~~Recently the~~ *The* quadrivalent HPV vaccine has also been recommended for vaccination of males [CDC, 2011].

Moreover, a recent publication by the UK Medicines and Healthcare products Regulatory Agency (MHRA) reviewed the safety profile of Cervarix use in the UK from September 2008 to July 2012. No new safety concerns were identified and the number and nature of adverse drug reaction reports received was as expected after administration of at least 6 million doses of the vaccine in the UK. There was no indication that being vaccinated with Cervarix during pregnancy results in any congenital abnormality or is associated with a risk of spontaneous abortion (or miscarriage) or other adverse pregnancy outcomes [MHRA, 2012a; MHRA, 2012b].

- **Section 1.2. Rationale for the study and synopsis (Rationale for the study)**

In the US, the commercial distribution of *Cervarix* began in October 2009. However, the uptake of *Cervarix* in the US is lower than expected (234,710 doses were shipped in 2010; 153,730 *doses* in 2011; **134,720 doses in 2012; and between 100,000 and 150,000 doses are projected for 2013**). Hence, ~~there is a high risk that~~ the EPI-HPV-020 study will be unable to reach the target sample size during the scheduled recruitment period (Projected completion of the study: Q2 2015).

- Section 3. Study design and synopsis (Study design)

Table 1 Study groups and epochs foreseen in the study

Study Groups	Number of subjects	Age (Min/Max)	Epochs
			Epoch 001
exposed cohort	Approximately 240 (-30 to +45 day window) and 280 380 (-30 to +90 day window)	15-25 years	x
non-exposed cohort	Approximately 660	15-25 years	x

- Section 3.1. HPV vaccine coverage and pregnancy rate in the UK teenagers

In the UK public HPV immunization program (12-13 year olds), HPV vaccination coverage in the UK for 2009 was 88.1%, 86.0% and 80.1% for the first, second and third dose respectively. The coverage in the catch-up program for women (15-18 years old) was 62.2%, 54.2% and 31.8% for the first, second and third dose, respectively [Sheridan, 2009]. ***HPV vaccination coverage in the UK for 2010/11 was 89.0%, 87.6% and 83.8% for the first, second and third dose respectively [Health Protection Agency, 2012].***

- Section 3.2. Feasibility analysis and limitations of the study design and synopsis (Discussion of study design)

This is also the design agreed with the FDA for the ~~ongoing~~ study in the US (EPI-HPV-020).

- Section 5.2.1. The Clinical Practice Research Datalink *General Practitioner OnLine Database (CPRD GOLD)*

The CPRD ***GOLD*** is operated on a non-profit basis by the ~~UK Medicines and Healthcare products Regulatory Agency (MHRA)~~, containing coded longitudinal medical records from general practices and more recently from hospital-based care (e.g., Hospital Episode Statistics, HES).

A total of 4,621,799 patients from ~~646~~ **546** practices are currently active in the database.

Data are retrieved by means of the READ classification system; READ codes are a coded thesaurus of clinical terms, which are the basic means by which clinicians record patient findings and procedures in health and social care IT systems across primary and secondary care (e.g. ***general practitioner [GP]*** surgeries and pathology reporting of results).

Review of free text will be done by a GSK identified reviewer (Pallas, Health research and consultancy B.V) for completing extracted data; a final case ascertainment step will be performed as described in section **5.2.4.2**, 5.2.4.3 and 5.2.6.

- Section 5.2.4.2. Pregnancy outcomes

Post-term delivery (\geq 42 ***completed*** weeks of gestation)

The GSK Safety physician will also review the following pregnancy outcomes: abortions (spontaneous abortions, induced/therapeutic abortions, other abortions), stillbirths, neonatal death, for life births: pre-term and post-term delivery, small for gestational age at birth or large for gestational age at birth.

- **Section 5.2.4.3. Baby (live birth) characteristics and confirmation of birth defects**

All cases with an identified birth defect will be reviewed by a ~~blinded~~ GSK Safety physician using the birth defects classification by the CDC Metropolitan Atlanta Congenital Defect Program or MACDP [Centers for Disease Control and Prevention, 2004 and Centers for Disease Control and Prevention, 2007].

- **Section 5.2.5.1. First day of LMP**

If date of first day of LMP is missing or LMP date is equal to system date (± 2 days) but the EDD is completed in CPRD *GOLD*, the first day of LMP will be calculated as follows: ~~EDD-283280 days (283 days equal to the median of gestational age: 40 weeks + 3 days)~~ *(280 days equal to the median of gestational age: 40 weeks)*.

- **Section 5.2.6. Final case ascertainment step**

*After the first review by the GSK Safety physician (see section 5.2.4.2), individual data related to pregnancy outcomes defined as **spontaneous and other** abortions, stillbirths, **and** baby's death, ~~pre-term and post-term delivery, small for gestational age at birth or large for gestational age at birth,~~ will be reviewed by two pharmaco-epidemiologists specialised in teratology (see contributors) for final case ascertainment.*

- **Section 5.6.3.1. Cox proportional hazards model**

Lost-to-follow up (*de*-enrolment from CPRD *GOLD*).

- **Section 9. References**

Cancer Research UK - Cervical cancer statistics UK. **2008**.
<http://info.cancerresearchuk.org/cancerstats/types/cervix/>

Health Protection Agency (HPA; Immunization section). Annual HPV vaccine coverage in England in 2010/11. 22 March 2012. *Available at:*
<http://immunisation.dh.gov.uk/annual-hpv-vaccine-coverage-in-england-in-201011-report/>

International Society for Pharmacoepidemiology (ISPE). Guidelines for Good Pharmacoepidemiology Practices. GPP. *Revision 2, 2007*.
http://www.pharmacoepi.org/resources/guidelines_08027.cfm. Accessed: 13 September 2012.

Medicines and Healthcare products Regulatory Agency (MHRA). Drug safety update 2012(a); 6(4):H2.
<http://www.mhra.gov.uk/home/groups/dsu/documents/publication/con207196.pdf>.
Accessed: 11 March 2013

Medicines and Healthcare products Regulatory Agency (MHRA). MHRA Public Assessment Report: Cervarix HPV vaccine: update on UK safety at end of 4 years use in the HPV routine immunisation programme. December 2012(b). <http://www.mhra.gov.uk/home/groups/plp/documents/websiteresources/con213228.pdf>. Accessed: 11 March 2013

Sheridan A and White J. Annual HPV vaccine coverage in England in 2009/2010. Health Protection Agency Department of Health. Available at: http://www.dh.gov.uk/en/Publicationsandstatistics/Publications/PublicationsPolicyAndGuidance/DH_123795_118052

- **Appendix A, Section 2, Variables derived from CPRD GOLD**

32. First day of LMP:

First day of LMP=EDD-283*

**283 was replaced by 280 during the review of the pregnant women profiles by Pallas to fit the UK definition of the length of pregnancy (40 weeks).*

In Clinical or Referral file where medcode equals to 8879 (=Estimated date of delivery) and First day of LMP=EDD-283*

**283 was replaced by 280 during the review of the pregnant women profiles by Pallas to fit the UK definition of the length of pregnancy (40 weeks)*

33. First day of gestation:

Day of Gestation= EDD-283* OR First Day of Gestation calculated from data_field_2/3 (=estimated size in weeks + Unit). The EDD data field will be also retrieved. **283 was replaced by 280 during the review of the pregnant women profiles by Pallas to fit the UK definition of the length of pregnancy (40 weeks)*

34. Date of delivery: If no information available, the delivery date ~~form~~*from* CPRD GOLD MBL will be used or in *Patient file* mob/yob under baby identifier OR Entity type =115

44. Date of HPV Cervarix vaccination: If at least one dose of Cervarix is between 01Sep2008 and ~~31DEC2010~~ *30JUN2011*, the subject will be included in the eligible population.

- **Appendix B, Table 16 Cox Proportion Hazard analysis of spontaneous abortions: Sensitivity analysis (adjusted for other covariates)**

Other sensitivity analysis ~~with~~ *will* be reported in the same table layout
